Genes and gene by nutrient interactions play a major role in the regulation of NAFLD: Both genetic and environmental factors contribute to the onset and progression of NAFLD. NAFLD is a complex and heritable phenotype. Family-based studies have reported heritability estimates for NAFLD to be between 20% and 70%^{7,8}. Genome-wide and candidate gene studies have identified several genes associated with NAFLD⁸. Representative genes that were implicated in lipid metabolism and in the development and progression of NAFLD are shown in **Table1**. Few studies have shown that fructose affects lipogenesis in liver in a genotype-specific manner. Davis and colleagues found that Hispanic children with GG genotypes of *PNPLA3* SNP rs738409 were more inclined to accumulate fat in the liver as compared to children with CC or CG genotypes³. Similarly, another study investigating the effects of added sugars on liver fat found that individuals with TT of rs1260326 of *GCKR* increased their *de novo* lipogenesis by 44% during an oral fructose + glucose challenge⁴. However, none of the studies have shown the cumulative effects of SNPs on change in liver fat when exposed to fructose.

The genetic-specific effects of fructose on liver lipogenesis need to be studied as a first step towards individualized nutrition: This study assumes significance given that fructose affects liver lipogenesis differentially based on genotypes. It also paves the way towards individualized or personalized nutrition. Previous studies investigating the metabolic effects of fructose have been controversial. Some have shown significant effects of fructose on insulin sensitivity and *de novo* lipogenesis and triglycerides while others have shown no effects²³⁻²⁷. The range of these studies is wide, with the duration of the intervention ranging from 7 to 665 days, sample size ranging between 8 and 64 per group and amount of fructose per day ranging from 40 to 250g/d. For this exploratory and feasibility study we have selected the duration of 21 days, sample size as 12 per group and amount of fructose a ~0.75g/kg/day (equivalent to two sodas/per day).

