1.2 Name and Description of Investigational Product or Intervention

Acute fructose challenge: We will be using a fructose drink which will be prepared by dissolving 0.75g/kg fructose + 0.45g/kg glucose (NOW Foods, Bloomingdale IL), in 24oz water. This composition of fructose and glucose mimics the composition of fructose and glucose in 2 regular sodas²⁸ based on an approximate adolescent/adult body weight of ~65kg.

3-week intervention: We will provide each participant the same drink as described in the acute fructose challenge to be taken one per day.

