3.2 Allocation to Treatment Groups and Blinding (if applicable)

- We will allocate participants to high and low genetic risk groups

3.3

Study Duration, Enrollment and Number of Subjects

- The study has three phases. First phase will have 200 participants who will visit Human Research Core clinical suite and spend about 30 minutes providing saliva sample and completing a brief questionnaire.
- Second and third phases will have 48 participants. They will first undergo a MRI scan and next day a 3 hour acute fructose challenge (total time 3.5 hours) and then will consume sugar drink as given to them. They will visit again at the end of week 3 for further biomarker, MRI scan and fibroscan measurements.

3.4

Study Population

- Inclusion criteria: Caucasian children and young adults, overweight/obese, ages between 12 and 40 years and no history of alcohol abuse (> 7 drinks per week for a year) and no history of excessive fructose intake (> 14 drinks per week for a year). We will conduct a spot glucose check using a glucometer (Accu-Chek, Roche Diagnostics, CH) to check that the glucose levels of the participants are in the normal range (fasting < 100mg/dl, post meal < 140 mg/dl and random < 200 mg/dl).
- Exclusion criteria includes ages < 12 and > 40 years, healthy weight or morbidly obese, known alcohol abuse, not of Caucasian ethnicity, pregnancy, lactation, glucose levels > 100 mg/dl if fasting, > 140mg/dl if within 2 hours post meal and > 200 mg/dl if random, baseline MRI scan of liver fat fraction > 5%²⁷, and known diagnosis of diabetes, fructose intolerance and chronic kidney disease, use of lipid or uric acid lowering medications.

4

STUDY PROCEDURES (what will be done)

4.1

Screening/Baseline Visit procedures

Phase 1: Recruitment and screening of participants:

Screening: We will recruit 200 Caucasian children and young adults fulfilling our inclusionary criteria: ages between 12 and 40 years, overweight or obese, no history of fructose intake > 14 drinks per week and alcohol abuse (> 7 drinks per week for a year). Height will be measured to the nearest 0.1 cm by a stadiometer situated against the wall in an upright standing position. Height and weight recorded will be used to calculate BMI as kg/m². We will match all participants for BMI (25kg/m² -32kg/m² or 85th-99th percentile).

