participate and that they should consult with their primary care physician. We will also advise them on diet and lifestyle that they can follow to minimize the risk. If non-liver adverse findings are reported during MRI, we will provide the participant with a letter that they can show to their physician.

Phase 2&3- visit 2- Oral fructose challenge: After their initial anthropometrics and Fibroscan measurements, they will undergo an oral fructose challenge using a protocol used by Hudgins et al¹³. The participants will be provided with a drink consisting of 0.75g/kg fructose + 0.45g/kg glucose dissolved in 24 Oz of water to be consumed within 15 minutes. An average overweight adolescent of 65 kg will consume 48.75g (65 x 0.75g/kg) fructose and 29.25g (65 x 0.45g/kg) of glucose which is similar equivalent to the sugars in two soda cans²⁸.

Blood and urine will be sampled at baseline and 1 and 3 hours after fructose ingestion. During the challenge period, no other beverage (except water) or food will be allowed.

Anthropometric measurements: Height will be measured using a portable stadiometer. Body composition and weight will be measured by bioelectric impedance technology using the Tanita Dual Frequency total Body composition analyzer (Tanita Inc., Arlington Heights, IL). Measurements will be conducted in a standing position, with subjects wearing light clothing and without shoes. Height will be measured to the nearest 0.1 cm by a stadiometer situated against the wall in an upright standing position. Height and weight recorded will be used to calculate BMI as kg/m². Waist circumference (WC) will be measured using a stretch-resistance tape at the midpoint between the lower margin of the least rib and the top of the iliac crest to the nearest 0.1 inch. Waist and hip circumferences will be measured to the nearest cm in a standing position. Sitting blood pressure (systolic and diastolic blood pressure) will be measured three times using the Omron digital blood pressure monitor (HEM907XL, Omron Healthcare Inc, Lake Forest, IL). The means of these measurements will be used for analysis. Well trained personnel in the UNC NRI Human Research Core will administer questionnaires as well as measure anthropometrics, by one staff member to minimize measurement variation and margin of error.

Questionnaires: The following six sets of questionnaires will be administered to the study participants.

- Personal Interview Form: Information related to demographics

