Medical care: According to the CDC report (cdc.gov/nutrition/data&statistics), ~51% of Americans drink at least one soda or other type of sugar-sweetened beverages on a given day. Higher prevalences have been found in Southern states and in adolescents. Therefore, we don't anticipate any medical issues as three sugar drinks per day is conforming to the present frequency. However, we will refer to our resident clinician in case any participant wants to consult or has concerns. The participant will be free to withdraw anytime during the study with no repercussions.

Dietary compliance: Dietary compliance will be assessed by the use of frequency questionnaires and three 24-hour diet recalls (Phases 1, 2 and 3).

Dietary guidance: Since each participant will take daily ~500 Kcal more than their normal daily dietary Kcal, we will provide guidance and options on how to cut down ~500 Kcal from elsewhere in their diet, especially in their consumption of sugary drinks.

Biochemical phenotyping: Liver function markers (alanine transaminase (ALT), aspartate transaminase (AST), gamma glutamyl transferase (GGT)), uric acid and lipids (triglycerides and total cholesterol, high and low density lipoprotein (HDL and LDL) cholesterol will be measured in serum using standard reference methods via clinical chemistry analyzer. Serum lipids, uric acid and liver function markers will be measured in [name] lab.

A combination of transient elastography (Fibroscan) and serum liver function markers will be used which will increase the accuracy of non-invasive measurement of fat accumulation in NAFLD; and

Fatty Liver Index (FLI) is a surrogate measure for liver fat estimation. The FLI will be computed based on the following equation which was observed to be 84% accurate in liver fat estimation⁶

$$\text{Fatty Liver Index (FLI)} = \left(e^{0.953 \cdot \log_e(\text{triglycerides}) + 0.139 \cdot \text{BMI} + 0.718 \cdot \log_e(\text{ggt}) + 0.053 \cdot \text{waist circumference} - 15.745} \right) / \left(1 + e^{0.953 \cdot \log_e(\text{triglycerides}) + 0.139 \cdot \text{BMI} + 0.718 \cdot \log_e(\text{ggt}) + 0.053 \cdot \text{waist circumference} - 15.745} \right) * 100^6$$

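### Section 4.2 advises a flat cut of about 500 kcal/day to offset a drink that supplies about 312 kcal at the protocol's 65 kg reference weight, and counts the dose as three drinks when it is one

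*Combined protocol and SAP*

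**What the plan says.** Section 4.2 contains two statements about the amount of sugar given.

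- **Dietary guidance.** The extra intake is a single figure for everyone: "Since each participant will take daily ~500 Kcal more than their normal daily dietary Kcal". The remedy matches it: "we will provide guidance and options on how to cut down ~500 Kcal from elsewhere in their diet". The sentence ends by saying where the saving should mainly be found: "from elsewhere in their diet, especially in their consumption of sugary drinks".
- **Medical care.** No medical issues are expected, "as three sugar drinks per day is conforming to the present frequency".

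The dose is defined elsewhere. Sections 1.2, 4.2 (oral fructose challenge) and 7 give 0.75 g/kg fructose plus 0.45 g/kg glucose in 24 oz of water. Sections 1.2 and 7 give one such drink daily for the three weeks. The synopsis equates one drink with two soft drinks, and section 1 describes the "amount of fructose a ~0.75g/kg/day (equivalent to two sodas/per day"). Section 4.2 works an example: "An average overweight adolescent of 65 kg will consume 48.75g (65 x 0.75g/kg) fructose and 29.25g (65 x 0.45g/kg) of glucose". Section 1.2 states that the match to two sodas is "based on an approximate adolescent/adult body weight of ~65kg".

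Section 1.3 names weight gain as the only risk. Its response is advice to cut calories elsewhere and to avoid juices and other sodas during the intervention.

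**The concern.** A drink dosed per kilogram cannot add the same energy for every participant, and the protocol's own 65 kg example does not come near 500 kcal. The purpose of the advice, read with section 1.3, is to offset the drink so that participants do not gain weight. That calls for a cut equal to the drink's energy. A larger cut replaces a possible surplus with a possible deficit.

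This matters because of the design. All 48 participants receive the sugar drink and there is no control drink. The week 0 to week 3 comparison in section 6.3 therefore cannot separate the drink from energy restriction over the same weeks. A deficit would tend to work against the rise in liver fat that the study is looking for. The Fatty Liver Index, which section 6.1 lists with the main outcome, also contains BMI and waist circumference directly. Section 6.4 intends the data to be used to size a larger study, so an avoidable attenuation could carry forward.

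The count of three drinks is a separate inconsistency. Neither way of counting the dose, as one study drink or as two sodas, gives three.

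**Working it through.** **Inputs from the documents**
- Sugar per kg: 0.75 + 0.45 = 1.20 g/kg (sections 1.2, 4.2, 7).
- Frequency: one drink per day for 21 days (synopsis; sections 1, 1.2, 7).
- Reference weight: 65 kg (sections 1.2, 4.2).
- Eligible BMI: 25 to 32 kg/m², or the 85th to 99th percentile (synopsis; section 4.1).
- Stated surplus and advised cut: about 500 kcal/day each (section 4.2).

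**Assumptions, not in the documents**
- Energy factor: 4 kcal/g, with 3.6 to 3.75 kcal/g as lower alternatives.
- Adult heights: 1.60 to 1.80 m.

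**Step 1: the plan's own figures.** The 65 kg sugar load reproduces: 65 × 0.75 = 48.75 g and 65 × 0.45 = 29.25 g, total 78 g. The energy figure does not: 78 × 4 = 312 kcal, and 500/312 = 1.60. Lower factors widen the gap: 78 × 3.75 = 292.5 kcal and 78 × 3.6 = 280.8 kcal.

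**Step 2: weight at which 500 kcal would be right.** Energy per kg is 1.20 × 4 = 4.8 kcal/kg, and 500/4.8 = 104.2 kg. At 3.75 kcal/g it is 500/4.5 = 111.1 kg. At the adult BMI limit of 32, 104.2 kg corresponds to a height of √(104.17/32) = 1.80 m (1.86 m at 3.75 kcal/g).

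**Step 3: excess of the advised cut over the drink.** Excess = 500 − 4.8 × weight. The net daily balance is drink energy − adherence × 500, so a deficit starts once adherence passes drink energy/500.

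| Weight | Drink (kcal) | Excess at 4 kcal/g (3.75) | Over 21 days, full cut, 4 kcal/g | Adherence above which a deficit starts (4 kcal/g) |
|---|---|---|---|---|
| 50 kg | 240 | 260 (275) | 5,460 | 48% |
| 65 kg | 312 | 188 (208) | 3,948 | 62% |
| 72.25 kg (BMI 25 at 1.70 m) | 346.8 | 153 (175) | 3,217 | 69% |
| 80 kg | 384 | 116 (140) | 2,436 | 77% |
| 92.48 kg (BMI 32 at 1.70 m) | 443.9 | 56 (84) | 1,178 | 89% |

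At half adherence a 65 kg participant is in surplus: 312 − 250 = +62 kcal/day.

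**Step 4: sensitivity to adult height.** Ratio of advised cut to drink energy at 4 kcal/g, from BMI 25 to BMI 32:
- 1.60 m: 500/307.2 = 1.63 to 500/393.2 = 1.27
- 1.70 m: 500/346.8 = 1.44 to 500/443.9 = 1.13
- 1.80 m: 500/388.8 = 1.29 to 500/497.7 = 1.00

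**Step 5: the drink count.** The protocol equates 78 g with two sodas, or 39 g each. Three sodas would give 3 × 39 × 4 = 468 kcal, close to the stated figure. Three study drinks would give 3 × 312 = 936 kcal. Both statements in section 4.2 may therefore be left over from a three-soda dose, but that is inference; the documents do not say so.

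**The case against.** The arithmetic is not in dispute; the case on the other side is about consequence.

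- **The cut is optional.** Section 4.2 offers guidance and options, with no target that must be met. A deficit needs more than 62% adherence at 65 kg, and 69% to 89% for adults of 72 to 92 kg. It also needs participants to start in energy balance and the drink to displace no other food. This stands, and it is why no effect on liver fat is estimated. It does not make the stated amount right.
- **The gap is small for heavy adults.** At BMI 32 the ratio is 1.13 at 1.70 m and 1.00 at 1.80 m, which is near rounding for an approximate figure. This stands for them. It does not cover the 65 kg reference participant, where the figure is 60% too high, or lighter adolescents. Half of the 48 are to be children. The documents give no weight distribution, so the 50 kg row is illustrative.
- **An imbalance would be seen.** Body weight and composition are measured at weeks 0 and 3 (section 5), and section 4.2 plans diet recalls and frequency questionnaires. These could describe over-compensation afterwards. They do not correct the advice.
- **Both genetic groups get the same advice.** This is accepted. The point concerns the change over time, in a study that calls itself exploratory.
- **Three drinks is a slip.** This is also accepted. The dose is clear where it is defined, and the wording overstates it, so no added participant risk follows.

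**Conclusion.** The concern holds. The dietary guidance in section 4.2 is wrong as written: a flat cut of about 500 kcal/day does not match a drink supplying about 4.8 kcal/kg. At the protocol's 65 kg the advised cut is 1.6 times the drink's energy, an excess of 188 kcal/day or about 3,950 kcal over 21 days if the full cut is achieved. For adults of 1.70 m across the eligible BMI range it is 1.1 to 1.4 times, or about 1,180 to 3,220 kcal over 21 days. Only adults of about 104 kg or more receive 500 kcal.

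The energy factor is assumed, but the lower factors tried only enlarge the gap. The adult ratios rest on assumed heights. An actual deficit further requires high adherence, baseline energy balance and no displacement of other food. The direction of the effect on liver fat is plausible and its size is unknown. The drink count is a real but clerical contradiction and adds nothing to the seriousness of the point.

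**What to change.** Make two corrections in section 4.2.

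1. **Dietary guidance.** Replace the stated surplus with the energy in the drink, about 4.8 kcal per kg body weight, naming the 4 kcal/g factor used. Replace the advised cut with the same amount, calculated from baseline weight: 240 kcal at 50 kg, 312 at 65 kg, 384 at 80 kg. Keep the emphasis on sugary drinks, and state that sodas and juices given up under section 1.3 count toward the cut.
2. **Medical care.** Describe the dose as one study drink per day, equal to two sodas.

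The cost is these wording changes, including the short counting rule, and one multiplication per participant, using a weight already needed to prepare the drink. Dose, visits, sample size and analysis are unchanged. The safeguard against weight gain is kept, because the corrected cut equals the energy added. The first correction is the one that matters, and it can be made on its own.

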4.3 Follow- up procedures (by visits)

There is no follow-up

4.4 Unscheduled visits

- If the participant walks-in or plans to visit due to a health concern, we will refer the participant to our resident clinician or to a healthcare provider

4.5 Concomitant Medication documentation

- Sugary drinks consumption is very common, especially in this age group so we don't anticipate adverse reactions and need for medication. However, if needed, our resident clinician will be available to assist.
- All concomitant medication will be documented in our questionnaire and incorporated as covariates in our data analysis

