Study Objective(s)	
Our goal for this study is to generate preliminary data that is needed to support an application to NIH for funding of a larger, adequately-powered study to explore whether a set of genotypes, that increase the risk for nonalcoholic fatty liver disease (NAFLD), predispose individuals to increased de novo lipogenesis (DNL) and liver fat accumulation when exposed to fructose intake.
 
Primary Objective: To determine the impact of acute and prolonged exposure of fructose on hepatic lipid accumulation in adolescents and young adults (12-40 years) with high and low genetic risk for NAFLD using liver mass resonance imaging (MRI).
 
Secondary Objective: To explore the genetic-specific effects of fructose on markers of liver fat accumulation (fibroscan⁵ and fatty liver index⁶) and serum biomarkers related to lipids, uric acid and liver function.

Test Article(s) (If Applicable)	Sugar-Sweetened beverages
Study Design	
 a. We will screen 200 Caucasian children and young adults (12-40 years) to obtain 24 children and 24 young adults who are overweight/obese and drink <14 fructose drinks/week to participate in a 3-week fructose intervention study. The 200 participants will be genotyped for 10 SNPs involved in lipid metabolism and associated with increased NAFLD risk in previously published studies^{7,8}. We will select 12 children and young adults with 15 or more risk alleles and 12 children and 12 young adults with 6 or fewer risk alleles and provide them fructose + glucose⁹ drinks who will ingest one drink (equal to 2 soft drinks) per day for 3 weeks; b. We will measure liver fat using Liver MRI^{9,10} and transient elastography (Fibroscan)⁵ at week 0 and 3;

c. Data will be analyzed using paired and unpaired students T test to differentiate the responses between the time points and between the two groups, respectively.

Specific Aim2: Determine the impact of acute exposure of fructose on hepatic *de novo* lipogenesis

- Using the cohort described in Specific Aim1, we will conduct oral fructose tolerance test at week 0 and week 3;
- We will measure liver fat using Fibroscan
- Data will be analyzed using unpaired students T test and repeated measures ANOVA to differentiate the responses between and within the two groups, respectively.

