Specific Aim3: Determine the relationship between markers of DNL, liver fat accumulation and serum concentrations of lipids, uric acid and liver function markers before and after the fructose challenge

- We will measure serum concentrations of liver function markers, lipids and uric acid at week 0 and week 3;
- As in previous aims, data will be analyzed using students T test, and Pearsons correlations.

Subject Population	Inclusion Criteria
key criteria for Inclusion and Exclusion:	
 Subjects between 12 and 40 years No history of alcohol abuse (> 7 drinks per week) History of fructose intake of < 14 drinks per week Caucasian ethnicity BMI > 25kg/m² – 32kg/m² or 85th -99th percentile but otherwise healthy
	Exclusion Criteria
	
 ages < 12 and > 40 years Pregnant/lactating known alcohol abuse or fructose intake > 14 drinks per week not of Caucasian ethnicity glucose levels > 100 mg/dl if fasting, > 140mg/dl if within 2 hours post meal and > 200 mg/dl if random sample taking anti-hypertensive, anti-diabetic, uric acid and/or lipid-lowering medications known diagnosis of diabetes, fructose intolerance, chronic kidney disease, NAFLD or any liver-related disease, hypertriglyceridemia, polycystic ovary syndrome, hypothyroidism, obstructive sleep apnea, hypopituitarism and hypogandism BMI < 25kg/m² or > 32 kg/m² or < 85th or > 99th percentile Liver fat fraction >5% as per baseline MRI scan
Number Of Subjects	200 for first phase and 48 for the second and third phases
Study Duration	The first phase will be about 30 minutes and the second and third phase will be divided into two visits. Both visits in both phases will be about 3.5 hours each.
Study Phases	(1) Screening: We will screen participants for eligibility to participate in the study based on the inclusionary/exclusionary criteria specified above. The 200 children and young adults selected to participate will provide saliva which will be used to extract DNA and then genotype 10 SNPs. These SNPs are selected based on their association with de novo lipogenesis (DNL) or liver fat accumulation in previously published studies in Caucasians. We will select 12 children and 12 young adults with more than 15 risk alleles and 12 children and 12 young adults with less than six number of risk alleles.
Screening	
Study Treatment	
Follow-Up	

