	(2) Intervention: This part is divided into two phases. Each phase entails two visits. Phase2-visit 1: The 48 enrolled (24 in each of the high and low genetic risk group) will

visit the UNC NRI clinical suite run by the Human Research Core. They will be taken to the WakeForest imaging center for their baseline MRS scan.

Visit 2: Acute fructose challenge: The next day, they will have their initial anthropometrics and Fibroscan measurements. They will then undergo an oral fructose challenge using a protocol used by Hudgins et al¹³. The participants will be provided with a drink consisting of fructose (0.75g/kg body weight) + glucose (0.45g/kg body weight) dissolved in 24 Oz of water (equal to 2 soda cans) to be consumed within 15 minutes. Blood and urine will be sampled at baseline and 1 and 3 hours after sugar drink ingestion. During the challenge period, no other beverage (except water) or food will be allowed.

3-week intervention: The 48 participants will be provided with sugar drinks for the three week period. The drinks that need to be taken per day will contain fructose (0.75g/kg body weight) + glucose (0.45g/kg body weight) dissolved in 24 Oz of water (equal to 2 soda cans) which is similar to that provided during the acute fructose challenge⁷.

[figure not shown]
Addition of glucose to fructose in the challenge and 3-week intervention induces the lipogenic effects of fructose, alleviates gastrointestinal effects of fructose and mimics the real-life situation¹⁴. They will visit at the end of each week to collect drinks for the next week. In addition, participants will be given standardized meals for the day prior to the baseline fructose challenge. They will also be instructed to avoid alcohol, juices and sodas the previous evening.

Efficacy Evaluations	Changes in liver fat accumulation through MRI scans and fibroscan measurements, and serum concentration of other lipids, liver function markers and uric acid.
Pharmacokinetic Evaluations	N/A

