6.3 Statistical Methods

Each subject will be given sugar drink containing fructose and liver MRI scan with fibroscan measurements will be taken at baseline and end of 3 weeks. Data will be assessed using descriptive measures and confidence intervals. Paired t-tests and repeated measures regression analysis will be performed to explore the significant differences between week 0 and week 3. Also, for each subject, the area under the curve (AUC)¹³ will be computed and a linear regression with AUC as the response will be performed during the acute challenge.

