6.4 Sample Size and Power

Although our sample of 48 may not have the power to detect significant effects of fructose on liver fat, this group of 48 well-characterized individuals, focusing only on one ethnicity and one body weight group and specific genotypes will reduce variability and will generate meaningful data. We expect to apply these approaches and use these data to estimate sample size for larger studies with significant power to detect the effects of gene-nutrients interactions on NAFLD and other metabolic disorders.

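### Section 4.5 makes all concomitant medication a covariate, but gives no coding or time window and has no counterpart in the statistical methods; the rule should be replaced by a short pre-specified list

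*Combined protocol and SAP*

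**What the plan says.** Section 4.5 of the combined protocol and SAP contains the plan's only instruction on covariates: "All concomitant medication will be documented in our questionnaire and incorporated as covariates in our data analysis". The medication questionnaire in section 4.2 is broad, covering over-the-counter and traditional products as well as prescribed drugs.

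The statistical text does not take this up:

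- Synopsis, Study Design (first aim): "Data will be analyzed using paired and unpaired students T test to differentiate the responses between the time points and between the two groups, respectively".
- Section 6.3: "Paired t-tests and repeated measures regression analysis will be performed to explore the significant differences between week 0 and week 3". It adds a linear regression with the AUC from the acute challenge as response.
- Neither place names a covariate. Baseline liver fat, age stratum and sex are not mentioned as adjusters anywhere.

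Medication exclusions differ by place. The synopsis excludes people "taking anti-hypertensive, anti-diabetic, uric acid and/or lipid-lowering medications". Section 3.4 lists only "use of lipid or uric acid lowering medications". The exclusion list in section 4.1 names no medication.

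On size, section 6.4 begins: "Although our sample of 48 may not have the power to detect significant effects of fructose on liver fat". It says the data will be used to size a larger study.

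**The concern.** Section 4.5 promises an adjustment that section 6.3 does not contain. An analyst could satisfy it with one any-medication term, a handful of drug classes, or one term per product reported. The choice would be made after the medication data are seen, so the adjusted group difference is not pre-specified.

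Two costs could follow. First, terms that explain little of the outcome use up information in a sample of 48. Second, if drugs started during the 3 weeks of drinks are included, the model may adjust for something the intervention caused. Meanwhile two obvious candidates for adjustment are left out: the baseline value of the outcome, and the child/young adult stratum on which selection is based.

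What is at stake is the interpretability of the group contrast, and its value for planning the larger study. No stated power figure is affected.

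**Working it through.** **Inputs.** From the synopsis: 48 participants, 24 per genetic risk group. Assumed, because the documents do not say: no dropout; k medication indicators with 1 to 3 users each, placed without regard to group; no outcome variance explained by them; two-sided 95% intervals. The plan has no figure of its own to reproduce.

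**Step 1: which planned analyses the rule can affect.**

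- Paired and unpaired t-tests: none, since they take no covariates.
- Repeated measures model with complete week 0 and week 3 data and a random intercept: a person-level medication main effect is the same at both times and cancels from each person's change. The group-by-time contrast is the difference in mean change, with or without it. A numerical check with 24 + 24 people and 8 indicators gave identical estimates and standard errors. This fails if medication interacts with time, is coded as varying over time, or if week-3 data are missing.
- Regression of change, of the week-3 value, or of AUC on group: affected, as below.

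**Step 2: size in the affected models.** Without covariates, the variance of the group difference is σ²(1/24 + 1/24) = 0.0833σ², on 46 df. With k covariates unrelated to group, the expected variance inflation is 45/(45 − k), on 46 − k df. The ratio of interval widths is

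√(45/(45 − k)) × t(0.975; 46 − k) / t(0.975; 46), with t(0.975; 46) = 2.0129.

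For k = 8: √(45/37) × 2.0244/2.0129 = 1.1028 × 1.0057 = 1.109.

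Because sparse indicators are not a textbook covariate, the exact design-matrix variance was also averaged over random placements of 1 to 3 users per drug.

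| k | Variance increase (placements) | CI widening (placements) | CI widening (formula) |
|---|---|---|---|
| 1 | 2% | 1.2% | 1.2% |
| 2 | 5% | 2.3% | 2.4% |
| 3 | 7% | 3.6% | 3.7% |
| 4 | 9% | 4.9% | 5.0% |
| 8 | 21% | 10.4% | 10.9% |
| 12 | 34% | 16.9% | 17.9% |

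**Step 3: a drug with one user.** In these models the indicator fits that person exactly and removes them from the contrast. The variance becomes σ²(1/23 + 1/24) = 0.0851σ², a rise of 0.0851/0.0833 − 1 = 2%.

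**Step 4: when adjustment would pay.** The loss becomes a gain if (1 − R²) × 45/(45 − k) < 1, that is, if the drugs jointly explain more than k/45 of the residual variance: 2% for k = 1, 9% for k = 4, 18% for k = 8, 27% for k = 12.

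**Step 5: timing.** The questionnaires are described under visit 2, before the 3-week drinks. Section 5 lists no medication questionnaire among the week-3 measurements. Against that, the term concomitant, and the neighbouring sentence in section 4.5 about medication needed for adverse reactions, point to use during the drinks. The documents do not settle it.

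**The case against.** The sentence sits in a procedures section and can be read mildly. One any-medication indicator would satisfy it, at a cost of about 1% in interval width. The sample is aged 12 to 40 and otherwise healthy, many diagnoses are excluded, and section 4.5 itself expects no need for medication. Few drugs may turn up, and those that do might explain some variance. The study is exploratory and claims no power.

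Most of this stands, and it rules out several stronger readings that a reader might infer:

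- That every reported drug must become its own model term. The text does not fix the coding.
- That a drug with one user always drops that person from the contrast. This is true in a change-score, single-time-point or AUC regression, but not for a main effect in the complete two-time-point model.
- That the plan adjusts for post-baseline drug use. No time window is stated, and baseline-only use would not raise that objection.
- That the relevant drug classes are already excluded. All four appear only in the synopsis; section 3.4 names two and section 4.1 none.

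What the objection does not remove is the mismatch. The wording allows one term or a dozen, and the statistical section provides for neither.

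**Conclusion.** The concern holds in a limited form. Section 4.5 sets an open-ended covariate rule that the methods in the synopsis and section 6.3 do not implement, so the adjusted analysis is not pre-specified. That conclusion needs no assumption about how many drugs are reported.

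The precision cost is conditional. It arises only if separate indicators enter a change-score, week-3 or AUC regression, and it depends on a drug count that the documents do not give. With few drugs it is small; it becomes material from about eight uninformative indicators upward. Taking the upper end of the table as the expected loss would go beyond the documents. Conditioning on post-baseline use is a possibility, not a stated plan.

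Priority is modest. The change is worth making because it is cheap and because section 6.4 intends these estimates to inform a larger study.

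**What to change.** Replace the covariate clause in section 4.5 with a statement that medication use is recorded and summarised by genetic risk group, with the time window given. In section 6.3, specify:

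- The between-group regression of the week-3 outcome, or of its change, adjusts for age stratum (child or young adult, with the dividing age stated) and the baseline value of the outcome.
- The unadjusted comparison of change is reported alongside. The genetic groups are not randomised and may differ at baseline, in which case the baseline-adjusted and change-score results can legitimately disagree.
- Medication use enters only a sensitivity analysis, with its coding fixed in advance and baseline use kept separate from use that begins during the 3 weeks.

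Reconcile the medication exclusions in the synopsis, section 3.4 and section 4.1.

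The cost is wording only: the adjusters use data already collected, and no visit, measurement or sample size changes. The downside is that rare medication effects are not modelled in the main analysis.
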